2. OVERVIEW OF STUDY DESIGN

2.1 STUDY AIMS

SCRIPT's Specific Aims are as follows:

Aim 1: *Evaluate the feasibility of an ACT stigma intervention* compared to standard of care via a 2-armed RCT of 100 HIV-positive Russian PWID on the following outcomes:

- a. Primary: Satisfaction with the intervention at 1 month
- b. Secondary:
 - a. Participation in three intervention sessions;
 - b. Fidelity to the intervention, using the Adherence Raters' Manual for Stigma Treatment Study (Kohlenberg et al, 2004) and an intervention adherence score

Aim 2: *Measure changes in internalized stigma*

- a. Primary: HIV Stigma via the Simbayi HIV internalized shame scale at 1 month;
Substance Use Stigma via Modified Substance Abuse Self-Stigma Scale at 1 month
- b. Secondary:
 - a. Any initiation of HIV care (ART) at 6 months
 - b. Engagement in substance use care at 6 months
 - c. Change in last 30 days injection drug use at 6 months
- c. Exploratory
 - a. Depression as measured by the PHQ-9 at 6 months
 - b. Anxiety as measured by the GAD-7 at 6 months
 - c. Intersectional stigma as measured by both substance use stigma and HIV stigma scales at 6 months
 - d. Psychological flexibility as measured via the Acceptance and Action Questionnaire at 6 months

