3.5 SCHEDULE OF DATA COLLECTION

		Phone Screener	Screener and Baseline		ACT Sessions 1-3	1-month assessment (4 weeks)	6 month visit (24 weeks)
			In-person Screener	Baseline			
Screening	Verification of HIV and hx of IDU	X	X				
	Screening Questions	X	X				
Enrollment	Sign Informed Consent		X				
	Complete contact information/verify numbers			X			
Assessment	Baseline Study Assessment			X			
	1-Month Study Assessment incl ACT satisfaction questions					X	
	6-Month Study Assessment						X
	Interventionist Checklist				X		
Randomization	Randomization			X			
Intervention	Adverse Events			X		X	
	ACT Intervention				X		
Other	Compensate for Participation			X	X	X	X
	Provide Resource Card			X			
	Report Adverse Events			X	X	X	X
	Complete Tracking Forms		X	X	X	X	X

Control Group						
		Phone Screener	Screener and Baseline Visit		1 mo (4 weeks)	6 mo (24 weeks)
			In-person Screener	Baseline		
Screening	Verification of HIV and substance use	X	X			
	Screening Questions	X	X			
Enrollment	Sign Informed Consent		X			
	Complete contact information/verify numbers			X		
Assessment	Baseline Study Assessment				X	
	1-Month Study Assessment					X
	6-Month Study Assessment					X
	Randomization				X	
Other	Provide Resource Card				X	
	Compensate for Participation				X	X

	Complete Tracking Forms			X	X	X
--	-------------------------	--	--	---	---	---

3.5.A. VISIT WINDOWS

ACT Intervention Session Windows for Intervention Group

1st ACT Session

- Window open: 1 day post baseline
- Target date: 7 days post baseline
- Window close: 31 days post baseline
- Window length: 30 days

2nd ACT Session

- Window open: 8 days post baseline
- Target date: 14 days post baseline
- Window close: 29 days post baseline
- Window length: 21 days

3rd ACT Session:

- Window open: 15 days post baseline
- Target date: 21 days post baseline
- Window close: 36 days post baseline
- Window length: 21 days

Research Assessment Windows for Intervention and Control Group

Intervention Group 1 Month (4-week) Visit

- Window open: 16 days post first group session
- Target date: 30 days post first group session
- Window close: 90 days post first group session
- Window length: 74 days

Intervention Group 6 Month (24-week) Visit

- Window open: 151 days post first group session
- Target date: 180 days post first group session
- Window close: 240 days post first group session
- Window length: 89 days

Control Group 1 Month (4-week) Visit

- Window open: 16 days post baseline

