5.2 FOLLOW UP ASSESSMENTS

Phone assessments will be permitted for 6 month assessments, as a last resort, for participants who are unable to come in-person. The 1 month assessment will take about 45 minutes, the final assessment at 6 months will take about 60 min.

Administered Assessment	Baseline	1-Month	6-Month
Demographics	X		
ART Use and Adherence	X	X	X
HIV Sex Risk Behaviors	X	X	X
HIV Risk Categories	X		
HIV Disclosure	X		X
HIV Stigma	X	X	X
Substance Use Stigma	X	X	X
Substance Use Daily Life Experience (SRS)	X		
Acceptance and Action (AAQ-II – SA)	X	X	X
Patient Health Questionnaire (PHQ-9)	X	X	X
Anxiety (GAD-7)	X	X	X
Partner Violence and Sexual Assault	X		
Alcohol Use: AUDIT-C	X		
Perceived Alcohol Stigma	X		
Drug Use	X	X	X
Overdose	X		X
Social Support Scale	X		X
VR-12 Health Survey	X		X
Health Care Utilization	X		X
Abbreviated PTSD Checklist	X		
Involvement with Police	X		X
[‡] Satisfaction with the Intervention		X	
*HIV Testing History	X		
^a COVID-19 testing history, risk behaviors, and perceptions			X

[‡]Intervention group participants only

*If this information is not collected at baseline, RAs will collect this information at a later study visit.

^a Not administered to all 6-month participants

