8. STATISTICAL ANALYSIS

This study will use an intent-to-treat analysis that includes all participants according to their randomized assignment. Descriptive statistics will be calculated for variables at baseline and each follow-up time to assess whether there appear to be any differences across treatment arms.

Our Specific Aims are to compare the effects of SCRIPT and standard of care on following outcomes:

Aim 1: Evaluate the feasibility of an ACT stigma intervention compared to standard of care via a 2-armed RCT of 100 HIV-positive Russian PWID on the following outcomes:

- Primary: Satisfaction with the intervention at 1 month
- Secondary:
 - Participation in three intervention sessions;
 - Fidelity to the intervention, using the Adherence Raters' Manual for Stigma Treatment Study (Kohlenberg et al, 2004) and an intervention adherence score

Aim 2: Measure changes in internalized stigma

Primary:

- a. HIV Stigma via the Simbayi HIV internalized shame scale at 1 month;
- b. Substance Use Stigma via Modified Substance Abuse Self-Stigma Scale at 1 month

Secondary:

- a. Any initiation of HIV care (ART) at 6 months
- b. Engagement in substance use care at 6 months
- c. Change in last 30 days injection drug use at 6 months

Exploratory:

- a. Depression as measured by the PHQ-9 at 6 months
- b. Anxiety as measured by the GAD-7 at 6 months
- c. Intersectional stigma as measured by both substance use stigma and HIV stigma scales at 6 months
- d. Psychological flexibility measured via the Acceptance and Action Questionnaire at 6 months

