8.1 PRIMARY ANALYSES

The primary outcome for this aim is satisfaction with the intervention. We will calculate descriptive statistics for all variables at baseline and follow-up. Initial analyses will compare binary outcomes between groups using a chi-square test and comparing continuous outcomes (i.e. satisfaction scores) using two sample t-tests. Because ACT intervention is delivered in the form of group sessions, individuals within the same groups will be correlated. All analyses will use the intention-to-treat approach and analyze participants according to randomized group, accounting for intra-group correlation.

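### The between-arm t-test planned for satisfaction, the Aim 1 primary outcome, cannot be run because only the ACT arm is asked about satisfaction

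*Combined protocol and SAP*

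**What the plan says.** Section 8.1 states: "The primary outcome for this aim is satisfaction with the intervention". It then sets out the initial analyses: chi-square tests between groups for binary outcomes and, in the same sentence, "comparing continuous outcomes (i.e. satisfaction scores) using two sample t-tests". It adds that analyses are by intention to treat, according to randomised group, and account for intra-group correlation. It also says "We will calculate descriptive statistics for all variables at baseline and follow-up".

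The aims are framed as comparisons. The lead-in to section 8 reads "Our Specific Aims are to compare the effects of SCRIPT and standard of care on following outcomes", and Aim 1 there is "Evaluate the feasibility of an ACT stigma intervention compared to standard of care". Section 2.1 words Aim 1 the same way: "compared to standard of care via a 2-armed RCT of 100 HIV-positive Russian PWID on the following outcomes".

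The data collection is different. In the section 5.2 table, satisfaction appears at 1 month only and carries the footnote "Intervention group participants only". The intervention-arm schedule in section 3.5 lists "1-Month Study Assessment incl ACT satisfaction questions"; the control-arm schedule has a 1-month assessment with no mention of satisfaction.

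**The concern.** A two-sample test needs observations in both samples. Here one sample is empty by design: controls receive standard care (section 3.4), so they have no ACT sessions to rate, and they are not asked.

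Feasibility is half of the hypothesis in section 2.2, and this is the only test named for its primary outcome. If the text stays as it is, someone will have to decide after the data are in how satisfaction is analysed, on what denominator, and how membership of a therapy group enters the standard error. Those choices should be fixed in advance. What the plan leaves standing is a descriptive summary with no stated interval, although section 8.1 recognises that members of a therapy group are correlated and commits to allowing for it.

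**Working it through.** **There is no planned figure to reproduce.** The documents give no significance level, power, standard deviation, ICC or sample-size calculation for satisfaction.

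**Can the test be run?**

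| Input | Value | Source |
|---|---|---|
| Planned ACT participants | 65 | Section 2.4 |
| Planned control participants | 35 | Section 2.4 |
| Who is asked about satisfaction | ACT arm only | Section 5.2 footnote; section 3.5 consistent |
| Satisfaction scores, ACT | up to 65 | from the rows above |
| Satisfaction scores, control | 0 | from the rows above |

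The standard error of a difference in means is SD × √(1/n_ACT + 1/n_control). With n_control = 0 the second term is undefined. A two-sample t-test run on 65 values against none returned no statistic, degrees of freedom or p-value.

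**Could the two samples be anything other than the arms?**

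- The sentence that names the t-test begins with comparisons between groups, and the closing sentence of section 8.1 says participants are analysed by randomised group.
- Aim 1 names standard of care as the comparator.
- Reading the parenthetical as an example rather than a definition does not help, because satisfaction would still be an example of an outcome to be t-tested.
- Nowhere do the documents describe a control-arm satisfaction measure, a comparison within the ACT arm, or a single-arm inferential analysis.

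**How far does the problem reach?** Participation in three ACT sessions and fidelity of ACT delivery exist only where ACT is delivered, so no Aim 1 outcome supports a comparison with standard of care. The stigma scores and other Aim 2 measures in the section 5.2 table are collected in both arms.

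**What precision would a single-arm estimate have?** This illustrates the replacement analysis; it does not measure the defect. Inputs are 65 scores in 13 groups of 5 (sections 2.4 and 3.1) and assumed ICCs.

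- Design effect: DE = 1 + (5 − 1) × ICC
- Degrees of freedom: 13 − 1 = 12, with t(0.975, 12) = 2.179
- 95% half-width in SD units: 2.179 × √(DE/65)

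| ICC (assumed) | DE | Half-width (SD) |
|---|---|---|
| 0 | 1.00 | 2.179 × √(1.00/65) = 0.270 |
| 0.05 | 1.20 | 2.179 × √(1.20/65) = 0.296 |
| 0.10 | 1.40 | 2.179 × √(1.40/65) = 0.320 |

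The same t quantile is used in every row, so the change from 0.270 to 0.320 comes from the ICC alone.

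**The case against.** The strongest objection is about weight. The contradiction cannot corrupt a result, because the test simply fails. Descriptive statistics for every variable are already promised, and description is a normal way to report a feasibility outcome. Section 8.1 also already commits to accounting for intra-group correlation, so what is missing is the method and not the intention. No data and no Aim 2 inference are harmed. All of that is true. It does not alter the fact that the one test named for a primary outcome is impossible, or that no interval or clustering method is specified in its place.

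Some smaller points stand:

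- The control-arm table in section 3.5 looks displaced in the extracted text, so it only corroborates. The section 5.2 footnote carries the point alone.
- The 65 is a planning figure, not a strict ceiling. Exact 2:1 allocation of 100 gives 66.7 to 33.3, and section 3.2 provides for enrolment beyond the planned size. The control count stays at 0 either way.
- The half-widths depend on assumed ICCs and on using 12 df. At ICC 0 with 64 df the half-width would be about 0.25 SD. They carry no weight in the conclusion.
- Collecting a comparable satisfaction-with-care measure in both arms would preserve the comparison. That needs new data, and it would measure something other than satisfaction with ACT.

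**Conclusion.** The concern holds: the plan is wrong as written and must be corrected. The Aim 1 primary test has up to about 65 scores in one arm and 0 in the other, and no reading of the documents makes it workable. The comparison with standard of care is equally empty for the Aim 1 secondary outcomes. This conclusion rests only on sections 8.1 and 5.2 and needs no assumption. The illustrative single-arm precision, 0.27 to 0.32 SD, does rest on assumptions: ICC from 0 to 0.10, a score from all 65, and 13 equal groups. The defect is confined to Aim 1.

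**What to change.** In section 8.1, replace the between-arm test for Aim 1 with single-arm estimates:

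1. **Satisfaction:** the mean 1-month score among ACT participants who have one, with a 95% confidence interval allowing for therapy group (for example, a group-level standard error with number of groups minus 1 df). Report how many of those randomised to ACT have no score.
2. **Participation:** the proportion of all randomised to ACT who attended all three sessions, with a similar interval. State whether the individual make-up second session (missed-visits subsection within section 4.6) counts, and how people who never attend are placed in a group for the interval, for example in the first group they were scheduled for.
3. **Fidelity:** session-level summaries of the interventionists' checklist and of the rater scores on the coded subset of recordings (sections 3.3.A and 3.6).

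Remove the standard-of-care comparator from Aim 1 in sections 2.1 and 8, and limit the comparative lead-in of section 8 to Aim 2. Between-arm tests for Aim 2 must still account for intra-group correlation, as section 8.1 requires. Setting a feasibility benchmark before the satisfaction data are examined would be useful but is secondary.

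The cost is an amendment to protocol and SAP wording, with no new data.

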2.4 STUDY DESIGN

SCRIPT is a Randomized Controlled Trial (RCT) among 100 HIV+ PWID, which aims to test the feasibility of the SCRIPT intervention and evaluate its effectiveness on the reduction of internalized stigma as well as self-reported entry into substance abuse treatment or initiation of ART. Eligible participants will be randomly assigned into one of two groups: 1) Control group receiving CSO site standard of care or; 2) ACT intervention. Both the intervention group and the control group will receive standard of care counseling and referral to addiction treatment and HIV treatment at the CSO sites. Following their baseline assessment, participants assigned to the intervention group will meet with the interventionist three times over one month in approximately 13 groups of 5 people each. All three sessions will be in groups, except for the occasional individual make-up 2nd session (more details in section 3.6B). Study outcomes will be assessed at 1 and 6 months (Figure 1).

Figure 1 illustrates the design of this 2-arm RCT with 65 participants in the SCRIPT intervention arm and 35 participants in the standard of care arm.

Figure: SCRIPT Study Design

Throughout the course of the study, participants in both groups will be expected to participate in three in-person assessments (baseline, 1 month and 6 months).

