3.4 CONTROL GROUP

Participants in the control group will receive standard care as normally provided to patients by civil society organizations. This could include information on HIV and substance use disorders, counseling, referral to addiction treatment clinics, and referral to HIV treatment clinics. They might also be given printed information, including phone numbers, on places that provide HIV medical care and substance use treatment.

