The ACT stigma intervention will be delivered by clinical psychologists. Supervision will be provided by site PI and an ACT trainer. Interventionists and supervisors will be trained by ACT trainers. To assess interventionist fidelity to ACT, we will use an ACT Fidelity Measure to rate the recorded intervention videos/tapes, with a focus on interventionist behavior and competency. The measure classifies three different targets of clinician behaviors, openness, awareness, engagement, as well as interventionist stance. This will also allow us to investigate how combinations of interventionist behaviors relate to outcomes and help train future interventionists in Russia and Russian speaking countries.

3.6.B MISSED VISITS

The following procedures will take place in the event of an intervention participant missing their group session. If they miss their:

1st session: We will schedule them into the next available group.

2nd session: We will ask them if they would like to participate in an individual make-up session. This will be an adapted session conducted by one of the interventionists who is trained specifically in this individual session. If they choose to not participate in the make-up session, they will still be scheduled for their 3rd session and for their 1-month and 6-month assessments.

3rd session: This will be a missed session, but they will still be invited for their 1-month and 6-month assessments.

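### Does the double use of *group* in section 8.1 leave the clustering adjustment undefined for controls and for ACT participants who never start?

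*Combined protocol and SAP*

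**What the plan says.** Section 8.1 is the whole of the between-arm analysis plan. It opens with simple tests: "Initial analyses will compare binary outcomes between groups using a chi-square test", with t-tests for continuous outcomes. It then gives the reason for going further: "Because ACT intervention is delivered in the form of group sessions, individuals within the same groups will be correlated". The operative sentence follows at once: "All analyses will use the intention-to-treat approach and analyze participants according to randomized group, accounting for intra-group correlation".

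The other relevant places are these:

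- Section 2.4 also calls the arms groups: "Eligible participants will be randomly assigned into one of two groups: 1) Control group receiving CSO site standard of care". It describes ACT delivery as "three times over one month in approximately 13 groups of 5 people each".
- Section 3.4 on controls: "Participants in the control group will receive standard care as normally provided to patients by civil society organizations".
- Section 4.5 starts the first ACT session only when five people randomized to ACT are available, so session groups are formed after individual randomization and within one arm.
- The missed-visits text in section 4.6 (numbered 3.6.B) says of a missed first session: "We will schedule them into the next available group". A missed second session may be made up individually.
- Section 8 on the analysis population: "This study will use an intent-to-treat analysis that includes all participants according to their randomized assignment".

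No section names a cluster variable, a model, a small-sample rule or an intraclass correlation (ICC).

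**The concern.** Read in isolation, the operative sentence puts *intra-group* straight after *randomized group*, so the nearest antecedent is the arm. Controls have no session group. Intention-to-treat also keeps ACT participants who never attend, and they have none either. A person who misses the first session changes group. The plan has no explicit code for any of these.

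What would be at stake is the inference on the Aim 2 outcomes: the two 1-month stigma primaries and the 6-month outcomes. Satisfaction, the Aim 1 primary, is collected in the ACT arm only (section 5.2), so control coding cannot affect it. If an analyst entered all 35 controls as one cluster, a cluster-robust variance would drop the control arm's sampling error, and a random-intercept model would add a full between-group variance to the control mean. The first is badly anti-conservative and the second badly conservative. A choice of that size, left until the data are in hand, would be a serious gap.

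**Working it through.** **Inputs from the documents.** 65 ACT and 35 control participants (section 2.4); about 13 ACT groups of 5, and 13 × 5 = 65 agrees. The 2:1 ratio in section 3.2 would give 66.7:33.3 of 100, which is within two people. The documents state no alpha, power, effect size, SD or ICC, so there is no planning figure to reproduce.

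**Assumptions.** ICC 0 to 0.20, two-sided 0.05, total variance 1, normal outcomes, independent controls.

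**Step 1: which cluster does the text mean?** The sentence before the operative one gives the ACT sessions as the source of correlation. Sections 3.4 and 4.5 show that controls are in no session group.

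- If *group* means session group, each control is independent.
- If *group* means arm, there are two clusters, the arm-level robust standard error is zero, and no test exists. No analyst could carry that out.
- Thirteen session groups plus the control arm as a fourteenth cluster mixes the two meanings. No section suggests it.

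**Step 2: variances at ICC 0.05.** The design effect in the ACT arm is 1 + (5 − 1) × 0.05 = 1.2.

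- True variance of the difference: 1.2/65 + 1/35 = 0.0185 + 0.0286 = 0.0470.
- Control arm as one cluster, robust: control residuals sum to zero, leaving 1.2/65 = 0.0185. The ratio is 0.0470/0.0185, about 2.55, and the normal-approximation error is 21.9%.
- Control arm as one cluster, random intercept: 1.2/65 + 0.05 + 0.95/35 = 0.0956. The ratio is 0.0956/0.0470 = 2.03, so the test is conservative.
- No adjustment: 1/65 + 1/35 = 0.0440. The correct standard error is √(0.0470/0.0440) = 1.034 times this, or 3.4% larger.

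**Step 3: type I error (%), 3,000 simulated trials per setting, no never-starters** (Monte Carlo standard error about 0.4 points at 5%).

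| Analysis | ICC 0 | 0.05 | 0.10 | 0.20 |
|---|---|---|---|---|
| Partially nested, Satterthwaite df | 4.9 | 4.3 | 4.8 | 5.4 |
| Mixed model, controls single, z | 4.7 | 4.3 | 5.5 | 6.2 |
| Mixed model, controls single, t with 12 df | 3.0 | 2.8 | 3.1 | 3.7 |
| Mixed model, controls in artificial fives, z | 4.5 | 3.9 | 4.4 | 4.6 |
| Robust variance, controls single, z | 5.9 | 5.3 | 6.5 | 7.1 |
| Unadjusted t-test | 5.1 | 5.4 | 6.7 | 9.1 |
| Control arm as one cluster, mixed, z | 3.6 | 2.4 | 2.2 | 1.2 |
| Control arm as one cluster, robust, t | 25.5 | 21.5 | 19.6 | 17.7 |

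The first five rows follow the plan and run from 2.8 to 7.1%. Only the last two rows give extreme errors among the adjusted analyses. A larger run (200,000 trials; ICC 0.01, 0.05, 0.10, 0.20; 12 df) gives 21.6, 19.6, 18.0 and 15.3% for one control cluster with robust variance, and 1.9, 1.6, 1.3 and 0.8% for the mixed version. Single-person controls with a small-sample correction give 5.0, 4.8, 5.1 and 5.1%.

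**Step 4: never-starters.** Suppose 10 of the 65 never attend. With controls single and ICC 0.05 to 0.20, z tests from the mixed and robust analyses give type I error of 4.7 to 6.5%, whether never-starters are single or share a cluster. Power moves more. At ICC 0.10, with an assumed 0.6 SD effect in attenders and none in never-starters, it is 56.1% (mixed, single), 64.5% (mixed, one never-starter cluster) and 61.6 to 65.3% (robust). It falls to 22.3% only if never-starters and controls share one no-group code in a mixed model, which again gives people a shared cluster when they never met as one.

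**The case for a change.** The strongest case for an amendment is that the freedom is real and cheap to remove. At an assumed 0.5 SD effect, single-person controls and the two one-cluster analyses fail to agree on p < 0.05 in 46, 51, 56 and 60% of trials at ICC 0.01, 0.05, 0.10 and 0.20. Single-person and artificial-group codings, both respectable, disagree in 8 to 11%. Never-starter coding moves power. A few sentences and a recorded session-group identifier would settle all of this before the data are seen.

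Part of this stands. The text does not fix the model, the degrees of freedom or the never-starter code, and two sound analysts could reach different p-values near 0.05. The large disagreement does not stand as evidence against the plan. It counts any three-way split, includes two analyses that err in opposite directions, and needs the hybrid coding that the text does not support; under the null it is 15 to 20%. The 8 to 11% partly reflects different degrees of freedom (about 44 against 18). With a normal reference it is about 5 to 7%, and under the null the two codings differ in about 2% of trials. That is the usual latitude when a plan states the adjustment but not the software call. No single method is required either, since several adequate ones hold their error near the nominal level.

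**Conclusion.** The concern does not call for a change. The double use of *group* is loose wording that its own context resolves: the correlation arises in ACT sessions, so the cluster is the session group, and people without one are independent. The plan already commits to accounting for that correlation and calls the unadjusted tests initial. Carried out in any of the sensible ways above, it gives type I error of about 3 to 7%. The alarming figures (about 15 to 25%, or about 1 to 4%) describe a coding mistake and not a reading of the plan.

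The remaining gaps are the model, the small-sample rule, and the code for never-starters and for those moved to a later group. A competent analyst fills these in the ordinary course. They bear mainly on power and borderline p-values for Aim 2.

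This conclusion rests on assumed ICCs up to 0.20, two-sided 0.05, groups of 5, and at most 10 never-starters. The comparison of codings used continuous outcomes. For the binary outcomes only the single-person-cluster robust analysis with small-sample correction was checked, at event rates of 0.2 to 0.5, where type I error was 4.9 to 5.4%; rarer events were not examined.
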